4.1 STUDY OUTCOME MEASURES

a) Degree of platelet inhibition measured with VerifyNow TM rapid platelet function analyser and also VASP flow cytometry at infarct vessel open time (also known as balloon time), 4 and 24-36 hours post dosing.

b) Index of Microvascular Resistance (IMR) measurement using pressure wire studies immediately following the PPCI procedure.

c) Measurement of thrombolysis in myocardial infarction (TIMI) flow grade using TIMI Frame Count.

d) ST Segment Resolution by ECG at 90-120 minutes post PPCI.

e) Infarct size by Peak Troponin at 24-36 hours post PPCI.

f) Final infarct size by CMR at three months in both patient groups (total of 100 subjects).

This study is not powered for clinical outcomes; however clinical and safety data will be recorded.

4.2 IN PATIENT SAFETY ENDPOINTS

- BARC definition for bleeding (see appendix 1)
- Target Vessel Failure
- Vital Status at Discharge

5 PARTICIPANT ENTRY

5.1 CONSENT

Consent will be a two-stage process for patients undergoing PPCI for STEMI. Verbal assent will be brief prior to the PPCI and first blood sample, so as not to lead to a reduction in the quality of patient care (MI outcomes are related to the door to balloon time with PPCI). A

shortened patient information sheet will be read to the patient and if verbal assent is gained it will be recorded in the clinical notes and the site file. This is in line with NRES guidelines that suggest that patients admitted with STEMI are considered as unconscious patients initially.

Following emergency PCI and IMR measurement, when the patient is pain free and has been able to rest, a full patient information sheet will be proffered and written consent sought. If the patient does not want to be part of the trial, he or she will be withdrawn from the study and future tests will not be performed. Treatment will continue in accordance with clinical guidelines. The patients' participation in the trial will last for 3 months. At the end of three months a Cardiac MRI scan will be performed unless there are specific contraindications. Vital status will be determined on discharge and at three months when patients turn up to have their cardiac MRI scan. If a patient fails to attend Cardiac MRI scan appointment in three months' time, a telephone call will be made to the relevant GP to determine the vital status of the patients.

5.2 ELIGIBILITY CRITERIA

All research subjects will be identified from STEMI patients admitted for PPCI at the Heart and Lung Centre in Wolverhampton.

5.3 RANDOMISATION

Potential patients will be reviewed by a member of the research team before randomisation to confirm eligibility. Once the eligibility of the patient is confirmed by the trial coordinators and the verbal assent is gained, randomisation will be carried out prior to patient's transfer to the cardiac catheter suite. Randomisation will be performed via a secure online web-based service. There will be a single password which will give access for randomisation for the trial on fully encrypted password-protected computers at the heart and lung centre, New Cross Hospital. The system is accessed via a secure connection (SSL) over the internet. This connection encrypts data between the user's internet browser and the server. Online randomisation is achieved by the trial coordinator entering a patient identifier (text field will be unique), own email address and the randomisation system password. Randomisation is by random permuted blocks to oral Ticagrelor or IV Cangrelor in 1:1 ratio. An email notification is generated displaying the chosen treatment group or code and sent to the email address given by the user randomising and the administrator email address. The administrator email address is the one provided when the system is set up (usually a trial coordinator or central trial email address). There is only one password and only members of the research team can perform a randomisation.

5.4 INCLUSION CRITERIA

- 1) Patients presenting with STEMI eligible for PPCI
- 2) Able to give verbal assent pre procedure and written consent following the procedure.
- 3) Age ≥ 18 years
- 4) No contraindication to Cangrelor or Ticagrelor

5) Thienopyridine naïve

Women of childbearing potential would be advised to use appropriate contraceptive measures to avoid pregnancy during treatment with the IMPS following the acute event.

If a patient gives verbal assent but is unable to provide a written consent at a later stage due to continued incapacitation, presumed consent will be continued. The reasons why a patient becomes incapacitated and becomes unable to provide a written consent will be recorded during data collection. As soon as the patient is able to provide written consent, written consent will be sort for continued participation or withdrawal as the patient wishes.

5.5 EXCLUSION CRITERIA

- 1) Be unable to provide verbal assent and written consent
- 2) Allergic to Aspirin or any of the $P2Y_{12}$ antagonists in the trial
- 3) Have pre-existing cardiogenic shock
- 4) Previous myocardial infarction
- 5) Have a concurrent septic or inflammatory disease e.g. rheumatoid arthritis, lupus, and pneumonia.
- 6) Already taking a P2Y₁₂ inhibitor
- 7) Known bleeding diathesis
- 8) Significant active bleeding
- 9) History of intracranial hemorrhage
- 10) Patients who are being treated with formal anticoagulation (Vitamin K antagonist, Factor II or Xa inhibitors) or have an indication for anticoagulation during the first four hours of the study period. Example is patients known to have atrial fibrillation, pulmonary embolism or deep vein thrombosis.
- 11) Known severe renal dysfunction requiring renal replacement therapy.

5.6 WITHDRAWAL CRITERIA

Patients are able to withdraw from the trial if they wish without the need to provide reasons and without their care being affected or compromised. Patients who decide to withdraw their consent to participate in the study will have all samples collected up to the time of withdrawal disposed of in appropriate manner. All information collected on the patient for the purpose of the study will be erased. The withdrawal shall be recorded in the study patient identification log. The treatment of the patient will continue in accordance with clinical guidelines should the participant choose to withdraw or not. If a patient dies after obtaining verbal assent but before gaining a written consent, they will still be included in the study and data collected up to the time of death will still be used. Patients who will need administration of glycoprotein IIb/IIIa inhibitors during or post PPCI procedure and patients who fail to have Cangrelor or Ticagrelor for unexpected circumstances will be withdrawn from the study and their data will not be collected.

Safety stopping criteria:

A participant would be withdrawn from the trial if the Clinician feels that continued participation would be unsafe for the participant.

This could include, but not restricted to:

- An anaphylactic shock
- An SAE occurring

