8. END OF STUDY

End of the study will be marked by the last patient's last visit samples when they have been analysed. The data will then be scrutinised, and finally an article summarising the study written and submitted to a peer-reviewed journal for consideration of publication. Positive trial results might lead to implementation of the use of intravenous Cangrelor in clinical practice.

Study termination

The safety monitoring committee/Steering Committee will meet on a regular basis. The trial will be terminated early if there is evidence of unexpected excess bleeding with cangrelor or severe or unexpected complications from the IMR procedure.

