9.2.2 Serious AEs

An SAE form will be completed and faxed to the Chief Investigator within 24 hours. However hospitalisations for elective treatment of a pre-existing condition do not need reporting as SAEs. Information about all serious adverse events will be collected and recorded on the Serious Adverse Event Report Form and faxed to the R&D Directorate at New Cross Hospital within 24 hours of learning of its occurrence.

All serious adverse events will be reported to the appropriate regulatory and ethical authorities.

Contact details for reporting SAEs [contact], attention [name] Please send SAE forms to: [name] [contact] (Mon to Fri 09.00 – 17.00)

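### Section 5.6 erases all study data of any patient who withdraws consent, even after written consent and with no safety exemption; this can bias the comparison, most plausibly for bleeding

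*Combined protocol and SAP*

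**What the plan says.** Section 5.6 sets the rule in two sentences. The first covers samples: "Patients who decide to withdraw their consent to participate in the study will have all samples collected up to the time of withdrawal disposed of". The second covers data: "All information collected on the patient for the purpose of the study will be erased". The withdrawal itself is entered in the patient identification log. No time limit is given, and safety data are not excepted.

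The surrounding sections fix when this can happen. Section 5.3 says that, after verbal assent, "randomisation will be carried out prior to patient's transfer to the cardiac catheter suite". Section 6.2.1 has the study drug given on that assent. Section 5.1 seeks written consent only after PPCI and the IMR measurement, and sets participation at three months. Of a patient who then declines, it says: "he or she will be withdrawn from the study and future tests will not be performed".

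On safety, Section 4.1 promises that clinical and safety data will be recorded, and Section 9.2.1 that all non-serious events will be. Section 9.2.2 says: "All serious adverse events will be reported to the appropriate regulatory and ethical authorities". Section 8 says: "The trial will be terminated early if there is evidence of unexpected excess bleeding with cangrelor".

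**The concern.** Deletion is triggered by a decision that patients make after randomisation and, in most cases, after treatment. The trial is open label, a tablet against an infusion, so they can know their arm and their early course. A patient who has bled may be more inclined to leave. If so, what is deleted depends on outcome, and it may differ by arm.

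Section 7 offers no protection. It names no analysis population, has no rule for missing data, and does not say whether withdrawn patients are replaced. The early-termination rule in Section 8 needs bleeding counts by arm, and those counts would come from a record that can shrink.

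**Working it through.** The plan has no figure to reproduce on this point. The sample size is 100 (50 + 50, consistent with 1:1 allocation), and Section 7.1 says it has no formal calculation behind it. The check is therefore one of sequence and consistency, followed by an illustration with assumed rates.

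**1. Order of events.** Verbal assent, randomisation, study drug, PPCI and IMR, written consent, ward sampling, discharge, CMR at three months (Sections 5.1, 5.3, 6.2 and Appendix 2). Any refusal of written consent, and any later withdrawal, comes after allocation and treatment.

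**2. What is lost.** Five of the six outcome groups in Section 4.1 (platelet inhibition, IMR, TIMI frame count, ST resolution, troponin) are complete by about 36 hours. Only CMR remains. A patient who formally withdraws consent in month two loses all five. Under Section 5.1, a patient who simply misses the scan triggers no erasure, and vital status is sought from the GP.

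**3. Which safety records survive.** SAE forms go out within 24 hours (Section 9.2.2), and nothing recalls them. But Section 9.1.2 places transfusion, tamponade and arterial complications outside the SAE definition, while Appendix 1 counts transfusion with overt bleeding, and tamponade, as BARC type 3. A substantial bleed may therefore generate no SAE report and, for trial purposes, exist only in the study record that Section 5.6 erases.

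**4. Bleeding illustration (all rates assumed).** Let b be the true risk, and let w_b and w_n be the proportions withdrawing consent among patients who bled and those who did not. Then

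observed risk = b(1 − w_b) / [b(1 − w_b) + (1 − b)(1 − w_n)].

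For b = 10%:
- 5% against 5%: 0.095 / (0.095 + 0.855) = 10.0%
- 20% against 5%: 0.080 / (0.080 + 0.855) = 8.6%
- 40% against 5%: 0.060 / (0.060 + 0.855) = 6.6%

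| True risk | w_b / w_n | Observed risk | Observed / true | Expected bleeds erased per 50 |
|---|---|---|---|---|
| 5% | 5% / 5% | 5.0% | 1.00 | 0.1 |
| 5% | 20% / 5% | 4.2% | 0.85 | 0.5 |
| 5% | 40% / 5% | 3.2% | 0.64 | 1.0 |
| 10% | 5% / 5% | 10.0% | 1.00 | 0.25 |
| 10% | 20% / 5% | 8.6% | 0.86 | 1.0 |
| 10% | 40% / 5% | 6.6% | 0.66 | 2.0 |
| 15% | 5% / 5% | 15.0% | 1.00 | 0.4 |
| 15% | 20% / 5% | 12.9% | 0.86 | 1.5 |
| 15% | 40% / 5% | 10.0% | 0.67 | 3.0 |

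The observed odds equal the true odds times (1 − w_b)/(1 − w_n). If the withdrawal pattern is the same in both arms, the odds ratio is unchanged and both absolute risks are understated. The comparison is distorted when the pattern differs by arm. With a true 10% in both arms and selective withdrawal in one arm only, the false difference is 10.0 − 8.6 = 1.4 points, or 10.0 − 6.6 = 3.4 points.

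**5. Precision if withdrawal is unrelated to outcome.** Assume a two-sided 5% test and 80% power. The detectable difference in SD units is √(2/n) × (1.960 + 0.842).
- n = 50 per arm: 0.200 × 2.802 = 0.56
- n = 45 (10% erased): 0.211 × 2.802 = 0.59
- n = 40 (20% erased): 0.224 × 2.802 = 0.63

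Power for a 0.5 SD difference falls from 71% at n = 50 to 66% at n = 45.

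**The case against.** The strongest defence is that erasure respects patients who were enrolled in an emergency on brief verbal assent. That carries real weight for those who decline written consent. It carries little for those who signed and left later, and the protocol does not give it as the reason. The information sheet and consent form are not part of the document reviewed, so what patients were told cannot be checked.

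Several stronger readings are tempting, and the documents do not support them.

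- A reader might infer that the comparison is biased. Bias is possible, not shown: it needs withdrawal to depend on arm and outcome, and no rates are given. It is also less plausible for platelet reactivity, IMR, frame count and troponin, since nothing says that patients learn these values before deciding.
- A reader might infer that every withdrawal triggers erasure. Only a patient's own withdrawal of consent does. Clinician-led withdrawal on safety grounds has no stated data rule. Patients needing glycoprotein IIb/IIIa inhibitors or missing study drug fall under a separate rule ("will be withdrawn from the study and their data will not be collected"), which is a different post-randomisation exclusion.
- A reader might infer that SAE reporting is defeated. Reports already lodged stay lodged, adverse-event recording ends at 36 hours, and clinical notes are not on their face study information. The exposure is the trial's own dataset and bleeds not classed as SAEs.
- A reader might infer that Section 5.1 contradicts Section 5.6. Section 5.1 is silent on data already collected, so the two can be read together, but they should be reconciled.
- A reader might see inconsistency in the rule for patients who die before written consent ("they will still be included in the study and data collected up to the time of death will still be used"). A patient who has died cannot withdraw, so there is none. Section 5.4 also keeps incapacitated patients in under presumed consent, so some of the sickest are not lost.

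Withdrawals are logged and each allocation is emailed (Section 5.3), so counts by arm may already be recoverable. These points narrow the concern. They do not supply a time limit or a safety exemption.

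**Conclusion.** The concern holds in this limited form. As written, Section 5.6 deletes completed outcomes and recorded safety events of randomised, usually treated patients whenever they withdraw consent, including after written consent. This sits badly with the commitments to record and report safety data in Sections 4.1, 9.2.1 and 9.2.2, and with the bleeding trigger in Section 8. The tension is one of implication, not an explicit clash of rules.

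The size is unknown. Over assumed true risks of 5% to 15%, the observed bleeding risk is 0.85 to 0.86 of the true risk if 20% of those who bled and 5% of others withdraw, 0.64 to 0.67 at 40% against 5%, and unchanged if withdrawal is unrelated to bleeding. In absolute terms this is a few events at most in an arm of 50. That matters mainly because a safety judgement in a trial of this size would itself rest on few events. The study is not powered for clinical outcomes, so no claim is made that a formal test result would change.

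**What to change.** Amend Section 5.6 and the patient documents as follows.

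1. After written consent, data and samples up to the withdrawal date are kept and analysed unless the patient asks for erasure.
2. Safety events already recorded are kept. This part needs to be aligned with Sections 4.1, 8 and 9.2. For patients who decline written consent it is subject to point 4.
3. Withdrawals of consent are reported by arm, separately for refusal of written consent and for later withdrawal.
4. For patients who decline written consent, reconcile Sections 5.1 and 5.6, and ask the ethics committee what minimal de-identified record (arm, date, reportable safety events) may be kept. That is the committee's decision and should not be presumed.

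The cost is a protocol and consent-form amendment needing ethics approval. The new rule would apply only to patients consented under it, so data from anyone enrolled earlier would remain subject to erasure.

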4. STUDY DESIGN

This is an open label randomised controlled pilot trial. We will enrol 100 patients (50 in each arm). We anticipate the conclusion of subject recruitment in 12 months from the study start date, with a further 6 months for data analysis and manuscript preparation. Patients in the intravenous Cangrelor arm will receive Cangrelor as an initial bolus dose given as per body weight followed by an intravenous infusion for no longer than three hours (The total dose of IV Kengrexal to be administered based on average body weight of 80 Kg is 510 micrograms/kg given over two hours), they will then switch to oral Ticagrelor given at maintenance dose of 90mg twice daily for 12 months. Patients in the oral Ticagrelor arm will receive Ticagrelor at a loading dose of 180mg followed by maintenance dose of 90mg twice daily for 12 months. All the 100 participants will undergo a CMR scan three months post PPCI.

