7. STATISTICS AND DATA ANALYSIS

All statistical analysis will be performed in collaboration with [name], Professor of biomedical statistics at University of Wolverhampton on fully encrypted password-protected computers at New Cross Hospital.

Continuous variables will be compared using parametric and non-parametric tests as appropriate. Dichotomous variables will be compared by Fishers exact test. Logistic regression analysis will be used to predict the significant independent predictors of poor outcome post angiography.

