7.1 Sample Size Calculation

A previous open label, multicentre study assessed the pharmacodynamics of Cangrelor in a number of patients with acute coronary syndrome (39 patients) (66). Our study is an open label single centre pilot trial planning to enrol 100 patients. Our study will provide the basis for power calculation for future similar studies. This study is a pilot study and not designed to test or determines clinical outcomes such as mortality, but rather we will be looking at the clinical efficacy of Cangrelor versus Ticagrelor in the context of platelet inhibition and effect on myocardial necrosis. Therefore, no formal sample size calculation has been conducted.

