9. ADVERSE EVENTS

9.1 **DEFINITIONS**

9.1.1 Adverse Event (AE): any untoward medical occurrence in a patient or clinical study subject. Adverse events will stop being recorded after 36 hours from the index admission.

9.1.2 Serious Adverse Event (SAE): any untoward and unexpected medical occurrence or effect that:

- Results in death
- Is life-threatening refers to an event in which the subject was at risk of death at the time of the event; it does not refer to an event which hypothetically might have caused death if it were more severe
- Requires hospitalisation, or prolongation of existing inpatients' hospitalisation
- Results in persistent or significant disability or incapacity
- Is a congenital anomaly or birth defect

Common expected post-procedural adverse events listed below are the conditions not going to be classed as SAEs:

- Acute renal failure requiring haemodialysis, peritoneal dialysis or haemofiltration
- Ventricular arrhythmia requiring direct-current (DC) cardioversion
- Atrial arrhythmia requiring intervention
- Significant heart block requiring temporary or permanent pacing
- Cardiac tamponade requiring urgent surgical intervention
- Cardiogenic shock requiring intra-aortic balloon pump or other assist device
- Emergency coronary artery bypass graft operation

- Arterial complications
- Blood or platelet transfusion

Medical judgement should be exercised in deciding whether an AE is serious in other situations. Important AEs that are not immediately life-threatening or do not result in death or hospitalisation but may jeopardise the subject or may require intervention to prevent one of the other outcomes listed in the definition above, should also be considered serious.

9.2 **REPORTING PROCEDURES**

All serious adverse events will be reported. Depending on the nature of the event the reporting procedures below will be followed. Any questions concerning serious adverse events reporting will be directed to the Chief Investigator in the first instance.w3433;

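### Section 5.6 removes two groups of randomised patients and stops collecting their data, so the arm comparisons are open to selection bias of unknown size and direction, and its scope against section 9 is not reconciled

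*Combined protocol and SAP*

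**What the plan says.** The first paragraph of section 5.6 ends with a rule for two groups: "Patients who will need administration of glycoprotein IIb/IIIa inhibitors during or post PPCI procedure", and patients who for unforeseen reasons get neither cangrelor nor ticagrelor. They "will be withdrawn from the study and their data will not be collected".

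Section 5.3 states that "randomisation will be carried out prior to" the patient's move to the catheter suite. Section 4 adds: "This is an open label randomised controlled pilot trial". Under 6.2.2, ticagrelor is given on the ward and cangrelor is started in the catheter lab.

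Section 7 names tests only: "Continuous variables will be compared using parametric and non-parametric tests as appropriate". It gives no analysis population, no intention-to-treat rule and no rule for missing data. Section 7.1 gives no sample size calculation, but says "Our study will provide the basis for power calculation for future similar studies".

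On safety, section 9.2 says "All serious adverse events will be reported", and 9.2.1 has all non-serious events recorded. Section 9.1.2 also says "Common expected post-procedural adverse events listed below are the conditions not going to be classed as SAEs"; the list includes transfusion, tamponade and arterial complications. BARC bleeding is a safety endpoint (4.2), and unexpected excess bleeding with cangrelor is a ground for early termination (section 8).

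**The concern.** Both triggers come after randomisation, and each can differ by arm and be linked to outcome.

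- **GP IIb/IIIa use.** Section 2.1 says that ticagrelor is not yet fully active at PPCI and that thrombus during PPCI matters for outcome. No criterion defines need, and the operator can know the arm. Use of these agents may therefore be partly a consequence of the treatment under test.
- **Missed drug.** The two drugs start at different places and times, so the opportunity to miss a dose differs by arm.

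The comparisons of platelet inhibition, IMR, TIMI flow, ST resolution, troponin and CMR infarct size would then no longer be between the groups that randomisation created. The variances meant for planning later trials would come from the same subset. IMR, the timed platelet samples and the three-month CMR cannot be obtained afterwards. Troponin is routine (6.5) and TIMI frame count is read from stored cine images (6.4), so those two could be retrieved.

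**Working it through.** **No figure of the plan's own to reproduce.** The documents state no removal rate, alpha, primary endpoint, SD or dropout allowance. Everything below is illustrative.

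**Inputs.** From the documents: 50 patients per arm, 1:1 (sections 4 and 5.3). Assumed: a two-sided 5% test; no true difference; a latent risk score whose correlation ρ with the outcome is 0.3 to 0.7; the highest-risk share p of each arm removed; removal rates as in the table. Section 2.1 describes falling use of GP IIb/IIIa agents, so low rates are plausible.

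**Formulas** (outcome in SD units, higher is worse; T = ticagrelor, C = cangrelor):

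- c = z(1−p) and λ = φ(c)/(1−p)
- shift in an arm's mean = −ρλ; bias (T minus C) = −ρ(λT − λC)
- retained variance v = 1 − ρ²λ(λ + c)
- SE = √[vT/(50(1−pT)) + vC/(50(1−pC))]
- type I error = Φ(−1.96 + |bias|/SE) + Φ(−1.96 − |bias|/SE)

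λ is 0.0494, 0.1086, 0.1950, 0.2743 and 0.3500 at p = 2%, 5%, 10%, 15% and 20%.

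**Worked case**, 15% against 5%, ρ = 0.7:

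- bias = −0.7 × (0.2743 − 0.1086) = −0.116
- vT = 0.824 and vC = 0.907
- SE = √(0.824/42.5 + 0.907/47.5) = 0.196
- type I error = 0.086 + 0.005 = 0.091

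| Removed, T vs C | ρ | Bias, SD (against cangrelor) | SE | Type I error |
|---|---|---|---|---|
| 5% vs 2% | 0.3 | 0.018 | 0.202 | 0.051 |
| 5% vs 2% | 0.7 | 0.041 | 0.196 | 0.055 |
| 15% vs 5% | 0.3 | 0.050 | 0.208 | 0.057 |
| 15% vs 5% | 0.7 | 0.116 | 0.196 | 0.091 |
| 20% vs 5% | 0.7 | 0.169 | 0.197 | 0.137 |

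Simulation of 20,000 trials with a Welch t-test gave 0.054, 0.090 and 0.136 for the three ρ = 0.7 rows.

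**What fixes the sign.** Swapping the rates reverses it. So does removing low-risk instead of high-risk patients: at 15% against 5% and ρ = 0.5 the bias goes from −0.08 to +0.08 SD. Equal rates give zero only if the mechanism is the same in both arms. With 10% removed in each arm, outcome-related in one and random in the other, the bias is 0.5 × 0.195 = 0.10 SD at ρ = 0.5.

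**Variance.** If removal takes the high-risk tail, retained variance is 0.983 to 0.907 at 5% removal and 0.974 to 0.859 at 10%. That is 2-9% and 3-14% too small for a later trial that analyses all randomised patients.

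**Section 5.6 against section 9.** Section 5.6 says that no data are collected on these patients. Sections 9.1 to 9.2.2 ask for all adverse events to be recorded and all SAEs to be reported, to 36 hours, and exempt nobody. The conflict is plainest for a patient who received study drug and then a GP IIb/IIIa inhibitor. Neither section says which prevails.

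**The case against.** **These agents contaminate platelet readings.** Section 2.1 says that aggregation runs through the IIb/IIIa receptor, and 6.3.1 says that VerifyNow measures aggregation. This stands for VerifyNow. It does not justify losing the other outcomes or the safety data, and it does not apply to patients who missed study drug.

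**The numbers will be small, and this is a pilot.** At 5% against 2%, 2.5 and 1 patients are affected, and the type I error hardly moves. The larger rates have no support in the documents. This stands as a limit on size. But section 7.1 offers the trial as the basis for later power calculations, and if few patients are affected, keeping them costs little.

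**Bleeding is covered by section 9.** A reader might infer that bleeds in these patients will be lost. The documents do not support that. Events taken off the SAE list in 9.1.2 remain adverse events and would be recorded under 9.2.1. Section 5.6 also makes an SAE a possible reason for withdrawal, so withdrawal and SAE reporting are expected to coexist. What remains is unclear scope, and BARC grading that is not assured.

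**GP IIb/IIIa use could still be counted.** A reader might infer that its use by arm cannot be reported at all. That is too strong. Each randomisation generates an allocation email (5.3), and the Appendix 2 schedule records concomitant medication at every timepoint. Section 5.6 orders erasure only when consent is withdrawn. Numbers removed by arm may be partly recoverable; the unmeasured outcomes are not.

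**Conclusion.** The point holds as a defect of design that should be fixed. The plan states an explicit rule that removes randomised patients after events that can depend on arm and outcome, and nothing in section 7 offsets it.

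The bias is a risk of unknown size and direction. Under the stated assumptions it runs from about 0.02 SD at low removal rates to 0.17 SD at 20% against 5%. For scale, 50 per arm gives 80% power for 0.56 SD at a two-sided 5% level.

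A reader might infer that the rule favours one particular drug. The documents do not support that: the sign depends on which arm loses more patients and on whether those removed are at high or low risk. Nor do they support saying outright that the variances will be too small; the 2-14% shortfall holds only if removal is outcome-related in the way modelled. On safety, the supported conclusion is that 5.6 and section 9 must be reconciled, because BARC bleeding bears on the termination rule in section 8.

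**What to change.** Replace the last sentence of the first paragraph of 5.6 with text to this effect:

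> All randomised patients who have not withdrawn consent, under 5.1, 5.4 and 5.6, stay in data collection and are analysed in the arm assigned. GP IIb/IIIa use (with time) and non-receipt of study drug (with reason) are recorded and reported by arm. BARC bleeding, AEs and SAEs are collected as in section 9.

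Then:

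- In the safety-stopping paragraph of 5.6, say that data collection not affected by the safety concern continues after a safety withdrawal. Say also that study procedures such as IMR are done only where the treating clinician judges them acceptable, and are otherwise recorded as not done, by arm.
- State the same population in section 7.
- Report VerifyNow with all readings. As a pre-specified supplementary analysis, set aside readings taken after a GP IIb/IIIa inhibitor, noting that this comparison is selected. Keep VASP and all non-platelet outcomes.
- Show the present exclusion as a per-protocol sensitivity analysis.

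No clinical rule on GP IIb/IIIa use changes.

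**Cost.** Amendment wording and a few CRF fields. The budget already covers tests for 100 patients, and the documents do not say whether withdrawn patients are replaced. Only if replacement was planned are there extra tests, at most £100 + £300 + 3 × £38.78 + 3 × £16 + £9 = £573.34 per retained patient. For 5 to 10 patients that is £2,867 to £5,733, or 4-8% of £68,834.

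**Downside.** The as-randomised comparison includes any effect of GP IIb/IIIa use, and some samples will be missing or hard to interpret.
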